◆ Pathophysiological Mechanisms and Importance of Gastroesophageal Reflux Disease (GERD)

Gastroesophageal reflux disease (GERD) is defined as a condition where stomach contents flow back into the esophagus, resulting in symptoms or mucosal injury. Common typical symptoms include heartburn or acid reflux, while atypical symptoms may include chest tightness, a sensation of a foreign body in the throat, hoarseness, or chronic cough. Clinically, GERD is a common chronic disease. In the United States, where symptoms occur at least once a week, up to 30% of adults are affected by GERD; in East Asia, the prevalence is 5-10%, but there is a growing trend in its incidence.

There are many possible pathogenic mechanisms for GERD, including lower esophageal sphincter (LES) dysfunction or structural abnormalities, ineffective esophageal motility, esophageal mucosal integrity defects, esophageal hypersensitivity, the formation of acid pockets after meals, the composition of gastric refluxate, and delayed gastric emptying. Currently, the most common diagnostic method involves observing damage to the distal esophageal mucosa through endoscopy or confirming abnormal gastric acid exposure via a 24-hour pH monitoring test. Based on the results of endoscopy and esophageal pH monitoring, GERD patients can be classified into two categories: erosive esophagitis (EE) and non-erosive reflux disease (NERD).

Repeated gastric acid exposure to the distal esophagus not only causes mucosal damage but may also lead to severe complications such as esophageal stricture, Barrett's esophagus, and esophageal adenocarcinoma. Statistics show that in the United States, medical and non-medical losses due to GERD exceed \$930 million annually. Therefore, GERD has become an important issue both clinically and in national public health policies in recent years.

◆ Disorders of gut-brain axis interaction in esophagus

Disorders of gut-brain axis interaction (DGBI) refer to gastrointestinal diseases that present with symptoms but no organic abnormalities, which were previously referred to as functional gastrointestinal disorders. In the recent Rome IV criteria , ¹¹ In the esophageal context, the Rome IV criteria define five conditions: functional chest pain, reflux hypersensitivity (RH), functional heartburn (FH), globus, and functional dysphagia. Epidemiologically, the prevalence of esophageal disorders related to gut-brain axis interaction is still not well understood. Past population-based

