than 4. The Lyon Consensus on the diagnosis of gastroesophageal reflux disease (GERD) states that an acid exposure time (AET) of less than 4% is considered physiological reflux, while an AET greater than 6% is considered pathological reflux. Additionally, if the total number of reflux episodes in 24 hours is less than 40, it is considered normal, while more than 80 episodes is considered abnormal.⁸ The combination of parameters such as acid exposure time (AET), number of acid reflux episodes, number of acid reflux episodes lasting more than five minutes, and the longest reflux episode duration can be used to assess the severity of reflux.¹⁹ By combining esophageal pH testing with impedance values, it is possible to detect the direction of reflux, as well as the reflux of weakly acidic, alkaline fluids, or gases.²⁰ During the detection period, patients are required to record all esophageal symptoms occurring during the esophageal pH-impedance testing. The physician will then compare these recorded symptoms with the reflux events documented by the pH-impedance monitor to calculate the association between reflux and symptoms (Symptom Association Probability, SAP, and Symptom Index, SI).²¹

Based on the above criteria for esophageal pH testing and endoscopic examination results, patients with esophageal reflux symptoms can be classified into erosive esophagitis, non-erosive reflux disease, esophageal hypersensitivity, and functional heartburn. Erosive esophagitis is characterized by visible mucosal damage at the distal esophagus during endoscopy; non-erosive reflux disease is identified by normal mucosa on endoscopy and pathological prolongation of the acid exposure time (AET) at the distal esophagus on esophageal pH testing; esophageal hypersensitivity presents with a normal AET, but the symptoms are associated with reflux events (refluxate may be acidic, weakly acidic, or weakly alkaline) as seen on pH-impedance testing; functional heartburn occurs when there are symptoms of gastroesophageal reflux disease, but both endoscopic examination and AET are normal. For disorders of gut-brain axis interaction, including functional chest pain, globus, and functional dysphagia, in addition to normal endoscopic and AET results, patients must not have significant esophageal motility disorders and must meet the diagnostic criteria related to esophageal symptoms, as well as the onset and duration of symptoms.

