Proton pump inhibitors (PPIs) are the primary medications used to treat gastroesophageal reflux disease. Although they are highly effective in improving typical heartburn symptoms in patients with erosive esophagitis,²⁷⁻²⁹ However, their effectiveness in treating non-erosive gastroesophageal reflux disease (NERD) is less than ideal. According to statistics, up to 50% of patients treated with proton pump inhibitors (PPIs) for suspected reflux symptoms still experience persistent symptoms.^{1,30} Studies have indicated that most gastroesophageal reflux disease (GERD) patients who are unresponsive to proton pump inhibitor (PPI) treatment have a normal acid exposure time (AET).³² In patients with heartburn who remain unresponsive to high-dose proton pump inhibitor (PPI) treatment, more than 90% are diagnosed with esophageal hypersensitivity or functional heartburn.^{31,32} In addition, patients with pathological reflux may also have concurrent esophageal brain-gut axis communication disorders. The complex pathophysiological mechanisms of gastroesophageal reflux disease (GERD) and the limited understanding of brain-gut interaction contribute to the poor treatment outcomes in such patients. Recent consensus suggests that non-reflux factors, such as altered perception or visceral hypersensitivity, may be associated with the refractory symptoms of the esophagus.³³

◆Treatment Strategies for Refractory Gastroesophageal Reflux Disease and Esophageal Brain-Gut Axis Communication Disorders

The treatment strategies for refractory gastroesophageal reflux disease (GERD) and esophageal brain-gut axis communication disorders remain unclear. Currently, it is believed that esophageal hypervigilance, anxiety, and autonomic arousal are the primary factors influencing the severity of symptoms and the response to reflux burden. The Esophageal Hypervigilance and Anxiety Scale (EHAS) has been recently validated in studies as an effective tool for assessing esophageal hypersensitivity.³⁴ Therefore, it is considered a helpful tool in diagnosing esophageal brain-gut axis communication disorders. Neuromodulators are medications used clinically to treat these disorders.

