Research Objectives

The objectives of this study :

Exploring the Effects of Cognitive Behavioral Therapy on Disorders of Esophageal Brain-Gut Axis Dysregulation.

Hypothesis:

- (1) Patients with disorders of esophageal brain-gut axis dysregulation often experience esophageal symptoms due to visceral hypersensitivity and esophageal hypervigilance, which can negatively affect their physical and mental health, sleep, and quality of life. Cognitive Behavioral Therapy (CBT) can help alleviate these symptoms and reduce their impact.
- (2) CBT has been shown to improve symptoms across different subtypes of disorders involving esophageal brain-gut axis dysregulation.

8. Research Methods, Procedures, and Execution Progress

1. Please describe in detail the research methods adopted in this project and the reasons for choosing them.
2. Potential challenges and solutions expected during the project.
3. If this is a continuous project, please also attach the progress report from the previous year or primary data.

Research Method

Participant

This project is a multi -center study. we will recruit cases from three medical centers in Taiwan, We plan to enroll a total of 120 participants, including 40 from our hospital, 40 from Kaohsiung Medical University Hospital, and 40 from E-Da Hospital.

This study is expected to last for 2 years, with the study period ending on December 31, 2025. We intend to recruit participants with esophageal symptoms related to disorders of the gut-brain axis communication from the Gastroenterology outpatient clinics.

Inclusion criteria for participants :

1. Age between 18 and 75 years, with clear consciousness and willingness to sign the informed consent form.

[figure not shown]
Version Date : (Version 8, 11/19/2024)

2. Participants with chronic esophageal symptoms related to esophageal-brain-gut axis communication disorders (such as heartburn, acid reflux, sensation of a foreign body in the throat, difficulty swallowing, chest pain, and chest tightness).

Exclusion criteria for participants :

1. Esophageal stricture, or a history of esophageal, gastrointestinal, or throat surgery.
2. Structural esophageal diseases (e.g., diverticula, esophageal rings), infectious esophagitis, erosive esophagitis, eosinophilic esophagitis.
3. Non-erosive gastroesophageal reflux disease or significant esophageal motility disorders.
4. A history or current diagnosis of esophageal, gastrointestinal, or other organ malignancies.

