For comparisons involving more than three groups, if the data are normally distributed, an ANOVA with post hoc tests will be conducted. If the data are non-normally distributed, the Kruskal-Wallis test will be applied. A p-value of less than 0.05 will be considered statistically significant.

Statistical analyses will be performed using SPSS 19 for Windows (SPSS, Inc., Chicago, IL, USA).

Clinical Significance and Originality of This Study

1. The originality of this study lies in its use of visceral sensitivity, mind-body connection, esophageal hypersensitivity, anxiety questionnaires, and functional gastrointestinal questionnaires to explore the effects of neuromodulators on diseases related to esophageal-brain-gut axis communication abnormalities. Patients with such conditions often experience more severe esophageal symptoms due to excessive visceral sensitivity and esophageal hypersensitivity.
2. This study aims to establish a model for Cognitive Behavioral Therapy (CBT) in disorders of esophageal brain-gut axis dysregulation. Our research examines the role of CBT in esophageal brain-gut axis dysregulation and refractory gastroesophageal reflux disease (GERD). The results obtained from this study will deepen our understanding of the pathophysiological mechanisms of esophageal brain-gut axis dysregulation and refractory GERD. The findings will help elucidate the etiology of refractory GERD, particularly when patients with GERD also present with esophageal brain-gut axis dysregulation, which leads to a lowered threshold for esophageal symptom perception. This condition can be reversed and improved through the aforementioned treatments. Furthermore, it will assist in early clinical intervention for patients with brain-gut axis communication disorders, enabling the establishment of personalized treatment strategies and the achievement of precision medicine for such patients.

9.Expected Work Items and Specific Outcomes

- (1) Please list the expected tasks to be completed within the execution period.
- (2) Expected contributions to academic research and other applied areas.
- (3) Expected training that participants will receive.

(1) Work items expected to be completed.

In this study, we will also explore the effects of Cognitive Behavioral Therapy (CBT) on disorders of esophageal brain-gut axis dysregulation, as well as its impact on physical and mental health and quality of life.

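### Must the protocol change because its significance text promises findings on refractory GERD and neuromodulators that its exclusions and arms cannot supply?

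*Protocol*

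**What the plan says.** Item 2 of Clinical Significance and Originality (section 8) presents refractory GERD as something the trial studies: "Our research examines the role of CBT in esophageal brain-gut axis dysregulation and refractory gastroesophageal reflux disease (GERD". It then narrows the claim to overlap patients: "The findings will help elucidate the etiology of refractory GERD, particularly when patients with GERD also present with esophageal brain-gut axis dysregulation". It closes the thought with "This condition can be reversed and improved through the aforementioned treatments". The Project Abstract (section 6) and the anticipated contributions (section 9) also list refractory GERD among the topics the results will illuminate. Item 1 of the same part of section 8 places the study's originality in exploring the effects of neuromodulators.

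The Background (section 7) says that "GERD patients can be classified into two categories: erosive esophagitis (EE) and non-erosive reflux disease (NERD". Its part on physiological tests adds that "non-erosive reflux disease is identified by normal mucosa on endoscopy and pathological prolongation of the acid exposure time (AET". Its part on the treatment dilemma describes the overlap group: "patients with pathological reflux may also have concurrent esophageal brain-gut axis communication disorders".

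Exclusion criterion 2 lists "infectious esophagitis, erosive esophagitis, eosinophilic esophagitis", and criterion 3 excludes non-erosive reflux disease. Criterion 7 excludes recent users of antidepressants or other psychiatric drugs. Criteria 10 to 12 exclude people allergic to tricyclics, SSRIs or PPIs. Steps to Follow randomises participants to six weekly sessions of CBT or six of lifestyle management. The Research Objectives and both hypotheses concern CBT in esophageal gut-brain disorders only.

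**The concern.** Read together, these places suggest that the trial claims more than it can deliver. If GERD consists of erosive and non-erosive disease and both are excluded, nobody with GERD plus a gut-brain disorder can be randomised, and nothing can be learned about that group. If neither arm gives a drug, nothing can be learned about neuromodulators. Three drug-allergy exclusions with no matching drug in the written steps add to the impression that aims, eligibility and interventions do not belong to the same study. The risk would be a report that extends a CBT result to patients barred from entry, or to a treatment nobody received. Sites would also be applying three entry criteria without a stated reason.

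**Working it through.** The plan gives no figure to reproduce. The check sets the claims beside the design.

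**Who can enrol.** The Background divides GERD into 2 categories. Exclusions 2 and 3 remove both, so 2 of 2 are barred. On that division the overlap group is ineligible. Two qualifications apply:
- The Background calls acid exposure below 4% physiological and above 6% pathological. It assigns 4% to 6% to neither, so nothing is concluded about those patients.
- The Background also reports that up to one third of functional-heartburn diagnoses made on 24-hour testing were later corrected to non-erosive disease. Some such patients may enter unrecognised. They could not be identified, so they could not support an overlap conclusion.

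**What is given.** There are 6 CBT sessions and 6 lifestyle sessions, 12 in all, and 0 of the 12 contains a drug. 0 of 2 arms gives a neuromodulator.

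**What each sentence claims.**

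| Place | Claim | Can the design address it? |
|---|---|---|
| Abstract, closing lines | GERD with refractory symptoms | Yes, on the looser reading |
| Significance, item 2, studied conditions | CBT in refractory GERD | Yes, on the looser reading |
| Significance, item 2, mechanisms | Refractory GERD | Yes, on the looser reading |
| Significance, item 2, etiology | GERD together with a gut-brain disorder | No |
| Section 9, contributions, item 1 | Refractory GERD | Yes, on the looser reading |
| Significance, item 1 | Effects of neuromodulators | No |

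The looser reading comes from the protocol. The Background reports that "most gastroesophageal reflux disease (GERD) patients who are unresponsive to proton pump inhibitor (PPI) treatment have a normal acid exposure time (AET", and that more than 90% of heartburn patients unresponsive to high-dose PPI have esophageal hypersensitivity or functional heartburn. Those patients are eligible. Of 1 + 3 + 1 = 5 sentences on refractory GERD, 4 are therefore ambiguous and 1 conflicts with the exclusions. The Abstract's next sentence already directs the guidance to patients with gut-brain disorders who do not respond to PPI. The sentence on reversal can refer to the lowered symptom threshold mentioned just before it. That is the mechanism in hypothesis 1, and it applies to eligible patients.

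**The allergy exclusions.** These are 3 of 12 criteria. No sentence in the protocol contradicts them; they only lack a stated reason. Functional heartburn is defined partly by non-response to antisecretory therapy, so a diagnostic reason for criterion 12 is conceivable. The Research Design Flowchart is not visible in the text available, so a matching step cannot be ruled out.

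**What depends on the two conflicting sentences.** The objective, hypotheses, arms, planned 120 participants (3 centres of 40) and statistical tests were each checked. None refers to GERD overlapping with a gut-brain disorder, or to a drug as a study treatment.

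**The case for a change.** The strongest case for a change is that the wording goes beyond background. Item 2 says what the research examines, and the reversal sentence anticipates a favourable result. The Abstract treats patients with GERD and a concurrent gut-brain disorder as distinct from those with a gut-brain disorder alone, so the looser reading cannot rescue the overlap sentence. PPI failure is not an entry criterion either, so even on the looser reading refractory patients are only an unspecified part of the sample. Correcting a few sentences would cost almost nothing, and the allergy criteria are operative text that sites must apply.

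Much of this stands. The overlap and neuromodulator sentences are wrong as written, and the protocol uses the term refractory GERD without fixing its meaning. What does not follow is harm to the trial. An analyst or author working from the objective, the entry criteria and the arms arrives at one conclusion: CBT against lifestyle management in esophageal gut-brain disorders without erosive or non-erosive reflux disease. Over-extension would require a report to ignore the trial's own eligibility table. For the allergy criteria, a missing rationale is a query at most.

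**Conclusion.** Two sentences in the significance text conflict with the design: one on GERD overlapping with a gut-brain disorder, and one on neuromodulators. They are slips in funding-style prose about anticipated value. The operative text already limits the objective to CBT in esophageal gut-brain disorders, and eligibility and arms agree with it. Four of the five mentions of refractory GERD can be read in a way that fits the enrolled population. Correcting the wording would gain nothing in power, bias or safety and would change no result, so no change to the plan is called for.

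This rests on two assumptions. The first is that conclusions will be drawn for the population actually enrolled, as the Research Objectives require. The second is that few candidates are lost to the three allergy exclusions. The protocol gives no number for this, and a small one is assumed.
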